## 5. TREATMENT OF SUBJECTS

Healthy subjects are not subjected to any type of treatment besides a lower leg muscle compressibility measurement. A summary of the measurements is given in figure 1.

*Figure 1: Summary of measurements. A total of 35 healthy volunteers will be included, who all will undergo rest measurements performed by three observers. These three observers will measure the anterior compartment (m. tibialis anterior) four times at four different locations (Right leg with tibial notch as internal landmark, right leg with interosseous membrane as internal landmark, left leg with tibial notch as internal landmark, and left leg with interosseous membrane as internal landmark). All healthy volunteers will then subsequently perform a treadmill exercise twice. After the first time, the right leg with tibial notch as internal landmark will be measured immediately, 1-minute, and at 5-minutes post exercise. After the second exercise the left leg will be measured immediately, at 1-minute, and at 5-minutes post exercise. Randomization will determine whether the right or left leg is measured first.*

### 5.1 Investigational product/treatment

All 35 healthy subjects will undergo four times four measurements in rest (m. tibialis anterior of both legs, using two different internal landmarks). Although the 'tibial notch' between the interosseous membrane and the tibial bone was previously suggested as the optimal landmark, recent data from our department suggest that the middle of the interosseous membrane is less variable. These four times four measurements in rest will each be done by three observers.

To measure the effect of exercise, compressibility will be measured immediately, one minute, and five minutes after a standard treadmill exercise at just one leg. The treadmill exercise and the corresponding measurements will be performed twice to include measurements of both legs. The measurements after exercise will be performed by only one observer.

### 5.2 Use of co-intervention (if applicable)

N.A.

### 5.3 Escape medication (if applicable)

N.A.

## 6. INVESTIGATIONAL PRODUCT

### 6.1 Name and description of investigational product(s)

Compremum Compartmental Compressibility Monitoring System, CPM#1

### 6.2 Summary of findings from non-clinical studies

For details we refer to the Investigator's Brochure (IB) page 18, chapter 4.

### 6.3 Summary of findings from clinical studies

For details we refer to the Investigator's Brochure (IB) page 25, chapter 5.

### 6.4 Summary of known and potential risks and benefits

There are no potential risks known for the CPM#1. Even so there will be no benefits for using the device outside of clinical setting.

### 6.5 Description and justification of route of administration and dosage

The CPM#1 device is an echo probe; thus, only pressure will be applied on the skin and ultrasound is used.

### 6.6 Dosages, dosage modifications and method of administration

N.A.

### 6.7 Preparation and labelling of Investigational Medicinal Product

N.A.

### 6.8 Drug accountability

N.A.

## 7. NON-INVESTIGATIONAL PRODUCT

Not applicable

## 8. METHODS

### 8.1 Study parameters/endpoints

#### 8.1.1 Main study parameter/endpoint

Inter-observer variance of compressibility among three observers using inter-class correlation coefficients (two-way random effects, single observer, absolute agreement).

#### 8.1.2 Secondary study parameters/endpoints (if applicable)

Intra-observer variance of compressibility within three observers using intra-class correlation coefficients (two-way random effects, single observer, absolute agreement).

Immediate, one minute, and five minutes post-exercise compressibility compared to the observer's rest measurement compressibility.

#### 8.1.3 Other study parameters (if applicable)

BMI, sex, age, leg dominance, NIAPS questionnaire, Experience questionnaire, internal landmark (notch or interosseous membrane)

### 8.2 Randomisation, blinding and treatment allocation

Randomisation:

The order of the measurements within a subject will not be completely randomised. However, we will randomize the order of the observers preventing bias due to fixed order of measurement. Also we will randomize the site of measurement where the observer will start (thus left or right leg) and approach (notch or interosseous membrane), by means of an online block randomization tool.

Blinding:

Observers will not be blinded to the results (i.e. the compressibility displayed in percentage), as distances cannot be made invisible during determining distances. However, after determining the distances, the device will calculate the CP value itself. Therefore this CP value is not influenced directly by the observer.

Observers will be instructed to not search for the previous measurements performed by previous observers. They are also instructed to not communicate the measurement results among each other.

Treatment allocation:

N.A.

### 8.3 Study procedures

This outpatient study will be conducted on 35 healthy volunteers. Participants will be placed comfortably in supine position. Measurements of compartment compressibility will be performed for each participant on both legs using the CPM#1. Exercise by means of a treadmill will be performed after all rest measurements have been performed.

#### Compartments:

Anterior compartment of the leg

#### Participant positioning:

- Measurement of anterior tibialis compartment
  - Participants will be asked to lie in supine position on an examination table (upper body will be slightly elevated at 5-10°) with a cushion below the head at least 5 minutes before measurement starts.
  - A triangular cushion will be placed below the knee (base width is 28cm, maximum height is 13cm)
  - Heel (with shoes on) will rest on the examination table.

#### CPM#1 measurements:

- Measurements will be performed according to the workflow depicted and explained in the instructions for use (IFU '20220222\_CPM#1\_IFU\_HVS\_E\_V1.1' – section 7 and 8), and summarized here below.

##### Step 1 - Manual investigation

- Identify the compartment for compressibility measurements

##### Step 2 - Location marking

- Mark the location for compressibility measurements with a medical marker.

##### Step 3 - Examination with CPM#1

- Place the probe on the target area
- Identify correct landmark
- Compress the compartment
  - Increase steadily the pressure applied by the CP probe to 80 mmHg.

##### Step 4 - Settings landmarks

- Set the outer and inner landmark of the 10mmHg-picture and 80mmHg-picture

#### Exercise:

- Participants will walk on a treadmill with standardized walking speed (5.0 km/hour) and slope (15%) for 5 minutes.

- Participants will then walk towards the bench and position themselves accordingly to previous anterior compartment measurements.
- Immediate, one minute, and five minutes post-exercise CPM#1 measurements will be performed at one leg.
- Exercise and post-exercise CPM#1 measurements will be repeated for the other leg.

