#### 4.4 Sample size calculation

As data on this device are scarce, a pragmatic sample size rationale is pursued based on previous studies that were made available to us by the company. Moreover, this study is not aimed at hypothesis testing, rather, we aim to estimate the ICC with certain precision. With the predecessor of CPM#1 it has been shown that an  $ICC \geq 0.75$  is achievable and thus demonstrated a good inter-observer reliability.

[figure not shown]
Measuring the left and right m. tibialis anterior in two directions, an expected  $ICC = 0.8$  (based on bench tests) and a one-sided 95% target confidence interval width of 0.05 based on three observers, a sample size of 140 is required. Since we measure 4 'samples' per participant (each leg the m.tibialis anterior at two different approaches, see section 5.1), we aim to include 35 healthy volunteers (140:4). We do not include dropouts in our calculation since we perform only one 90 minute session without follow-up. Participants who do not complete the

measurements will be replaced for new inclusions, such that we will have a complete data set of 35 participants in the end.

To power for the measurement directly after exercise, using dependent sample T-test with an expected effect size of 0.4 (based on results from bench test), an  $\alpha$  of 0.05 and power ( $\beta-1$ ) of 0.9, we would require 68 samples. Since the strict timing of the measurements after exercise only allows the measurement of one sample (one compartment using one approach), all participants will undergo two exercise sessions ( $2 \times 35 = 70$ ).

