### 10.2 Secondary study parameter(s)

The secondary endpoint of intra-observer variability will be the intraclass correlation coefficient (ICC) of agreement within three observers, four sites per subject, and four repetitions per measurement. The ICC will be assessed using a two-way random effects model. Both subjects and repetitions will be included as random effects. The repeated measures will be analysed for each observer separately and this agreement serves to address differences between observers. “Good reliability” classification will be reached if the lower bound of the computed ICC confidence interval does not fall below 0.75

The second secondary endpoint is the comparison between post-exercise (immediate, one minute, and five minutes) compressibility and rest compressibility. This will be analysed using a dependent sample t-test.

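### The post-exercise comparison pools one-bout and two-bout readings as 70 interchangeable pairs, with no bout or participant term and no defined rest comparator

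*Combined protocol and SAP*

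**What the plan says.** On timing, section 8.3 states: "Exercise by means of a treadmill will be performed after all rest measurements have been performed". Its Exercise steps have the participant walk for five minutes, return to the bench and have one leg read immediately, at one minute and at five minutes. Then: "Exercise and post-exercise CPM#1 measurements will be repeated for the other leg". No new rest reading before the second bout is described, nor any check that the second leg has returned to its resting value.

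On the comparison, section 8.1.2 gives the endpoint as "Immediate, one minute, and five minutes post-exercise compressibility compared to the observer", continuing with that observer's own rest measurement, in the singular. Section 5.1 provides four rest readings per site from each observer. For the ICC, section 10.1 separates the first reading from the mean of four. Section 10.2 does not say which applies to the exercise comparison.

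On size and analysis, section 4.4 plans the immediate reading "using dependent sample T-test with an expected effect size of 0.4" and, with power "of 0.9, we would require 68 samples". It reaches that number because "all participants will undergo two exercise sessions", counted as 2 x 35 = 70. Section 10.2 says of the three post-exercise comparisons: "This will be analysed using a dependent sample t-test". It names no term for bout, order, leg or participant.

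**The concern.** Half of the 70 pairs describe a leg after one bout. The other half describe a leg after two bouts, set against a rest value from before either. If the response after the second bout is not the same as after the first, the single pooled mean is an average of two different quantities, and the planned test gives no way to see this.

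The 70 pairs also come from 35 people, two legs each, and a t-test on 70 treats them as independent.

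The undefined comparator adds a choice that could be made after seeing the data, between a single rest reading and a more precise mean that is already being collected.

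**Working it through.** **Inputs from section 4.4:** paired t-test, standardised effect d = 0.4, alpha 0.05 (sidedness not stated), power 0.90, 68 samples required, 70 planned.

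**Assumed, not in the documents:** c, the extra response after the second bout, in SDs of the paired difference; and rho, the correlation between a person's two leg differences.

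**1. The plan's own figure.** The normal approximation gives (1.960 + 1.282)^2 / 0.4^2 = 10.51 / 0.16, so 66. The exact noncentral-t calculation, two-sided, gives n = 68 with power 0.902, and power 0.910 at n = 70. The one-sided calculation gives 55. So 68 reproduces with a two-sided test, and the arithmetic is sound if the 70 pairs are independent and equivalent.

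**2. What the pooled mean estimates.** With 35 pairs per bout: [35 d + 35 (d + c)] / 70 = d + c/2. Mixing two means also raises the SD to sqrt(1 + c^2/4), which is 1.005 at c = 0.2. For d = 0.4, n = 70, legs treated as independent:

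| Assumed c (SD) | Pooled mean (SD) | Power |
|---|---|---|
| -0.2 | 0.30 | 0.69 |
| 0 | 0.40 | 0.91 |
| +0.2 | 0.50 | 0.98 |

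The shift is always half of c, in either direction.

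**3. Two legs per person.** The mean of a person's two differences has variance (1 + rho)/2, so the person-level effect is 0.4 / sqrt((1 + rho)/2) with n = 35. Power is 0.90 at rho = 0, 0.81 at 0.3, 0.76 at 0.5 and 0.68 at 0.8.

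**4. First bout only.** With 35 pairs at d = 0.4, two-sided power is 0.63. The effect detectable with 90% power rises from about 0.40 to 0.56 SD.

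**5. Can the data show a bout difference?** The standardised contrast within person is c / sqrt(2(1 - rho)) with n = 35. For c = 0.4 SD it is 0.28 with independent legs (power about 0.37) and 0.40 with rho = 0.5 (power 0.63).

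**6. Comparator.** Take reading errors as independent with variance s^2. The error variance of a difference is s^2 + s^2 = 2.0 s^2 with one rest reading, and s^2 + s^2/4 = 1.25 s^2 with the mean of four. The documents do not say which kind of rest value the bench-test effect of 0.4 used, so I do not convert this into a new effect size.

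**The case against.** The case for leaving the plan alone has real content.

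- **Recovery.** The second bout cannot start until the first leg's five-minute reading is done, with the participant back in the measurement position. That leaves about five minutes of recovery, the same minimum lying time that section 8.3 asks for before measurement starts. The first leg's five-minute reading also gives some evidence of recovery after one bout. This makes a small c plausible, but it is not a check on the second leg.
- **Randomised order.** The Figure 1 caption says the leg read first is randomised. This keeps bout from being confounded with side. It does not change the fact that half of the pairs are second-bout readings.
- **Estimand.** The stated objective is the effect of exercise, not of a single bout, and pooling is explicit only in section 4.4. Section 10.2 does not say how legs are combined. That is fair, but the plan then needs to say which effect it reports, and the stated power depends on combining the bouts.
- **Importance.** This is a secondary endpoint of a 35-person pilot.

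A reader might go further and infer that carry-over inflates the false-positive rate of the t-test. The documents do not support that. If one bout has no effect, it leaves no residual to carry over. If a response appears only after two bouts, exercise does change compressibility, and a significant result is not false. A reader might also conclude that only the first bout should be analysed. Step 4 shows the price, with power falling from 0.91 to 0.63, so that is a trade-off and not a clear improvement.

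**Conclusion.** The point holds as a matter of what is being estimated and how it is modelled. By design, the pooled comparison mixes one-bout and two-bout readings against a rest value from before both, and the named test has no bout or participant term. This rests on the documents and on the plain fact that walking works both legs.

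The size of any bias is not known. It equals c/2, and nothing in the documents fixes the size or sign of c, which could be near zero. The 0.30 to 0.50 range rests on the assumed c of -0.2 to +0.2 SD. The loss of power from two legs per person likewise rests on an assumed rho. The documents therefore do not show that carry-over occurs or that the planned conclusion would be wrong.

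The stated 68 is arithmetically correct, and the primary endpoint is untouched because all rest readings come first. This is an inexpensive improvement to a secondary analysis.

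**What to change.** In section 10.2:

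- **Model.** Keep all 70 pairs and replace the plain t-test with a mixed model on the change from rest. Use fixed effects for bout, leg and time, and random effects for participant and for leg within participant. The last is needed because the three readings on a leg share one baseline.
- **Reporting.** Give the overall effect together with the bout 1 effect, the bout 2 effect and their difference, with confidence intervals. Present the bout 1 estimate (35 pairs) as a sensitivity result. Say in advance that the bout comparison has limited power (step 5), so a non-significant difference does not establish that there is no carry-over.
- **Comparator.** Define it as the mean of the same observer's four tibial-notch rest readings on that leg. The Figure 1 caption names that landmark only for the right leg, so state it for both.
- **Leg order.** The caption describes right leg first and left leg second, and then says the order is randomised. Reconcile these, because bout and leg can be separated in the model only if the order varies between participants.
- **Optional.** One tibial-notch reading on the second leg just before the second bout would measure carry-over directly.

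The cost is slightly more analysis work and a somewhat wider interval once two legs per person are accounted for. The optional reading adds one short measurement per participant.

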## Questionnaires

NIAPS questionnaire:

- Baseline (full questionnaire as appendix, '*F1-NIAPS Baseline*') with one additional question about leg dominance.

Experience questionnaire:

- Score 1-5 (full questionnaire as appendix, '*F1-Ervaringsvragenlijst v1.0*') questioning the intensity, how painful, the nuisance, the duration of the study and the non-invasive pressure measurements.

## 8.4 Withdrawal of individual subjects

Subjects can leave the study at any time for any reason if they wish to do so without any consequences. The investigator can decide to withdraw a subject from the study for urgent medical reasons.

### 8.4.1 Specific criteria for withdrawal (if applicable)

N.A.

## 8.5 Replacement of individual subjects after withdrawal

Measurements will only take place during one 90-minute session, thus there will be no withdrawal after data is collected. If participants withdraw before or during measurements, these participants will be replaced.

If for some reason more than one repetition is missed in one category, or one observer is missing, for that specific analysis this data will be excluded.

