### 10.1 Primary study parameter(s)

The primary endpoint of inter-observer variability will be the intraclass correlation coefficient (ICC) of agreement between three observers, four sites per subject, and four repetitions per measurement. The ICC will be assessed using a two-way random effects model. Both observers and subjects will be included as random effects. The first measurement for each location will be taken from every observer to calculate the ICC. Apart from that, the ICC will be measured using the average of the four repetitions of ratings, to estimate the effect on the ICC of repetitive measurements. “Good reliability” classification will be reached if the lower bound of the computed ICC confidence interval does not fall below 0.75.

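### Sections 4.4 and 8.5 describe different data sets, and both can discard valid readings that the planned random-effects model could use

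*Combined protocol and SAP*

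**What the plan says.** Section 4.4 makes no allowance for loss: "We do not include dropouts in our calculation since we perform only one 90 minute session without follow-up". Participants who do not finish the "measurements will be replaced for new inclusions, such that we will have a complete data set of 35 participants in the end".

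Section 8.5 ties replacement to withdrawal: "If participants withdraw before or during measurements, these participants will be replaced". It then adds a rule for records that stay in but have gaps: if "more than one repetition is missed in one category, or one observer is missing, for that specific analysis this data will be excluded". One missed repetition is therefore tolerated, and the exclusion applies only to the analysis concerned.

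Section 10.1 defines the primary ICC on single readings: "The first measurement for each location will be taken from every observer to calculate the ICC". An ICC on the average of the four repetitions is additional. The model is two-way with random observers and subjects, and good reliability requires a lower confidence bound of at least 0.75. Section 10.2 analyses intra-observer agreement for each observer separately. Section 8.3 places exercise after all rest measurements.

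The protocol does not define a category. It does not say whether a site or a whole participant is excluded, or what becomes of a replaced participant's readings. It plans no report of failed, missing or replaced measurements.

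**The concern.** Two analysts could build different primary data sets from this text. Under section 4.4 there are 35 complete participants and 140 complete samples. Under section 8.5 there may be participants with gaps, and fewer than 140 samples in a given analysis. Section 8.5 is also uneasy within itself: it says nobody will withdraw once data are collected, then provides for withdrawal during measurement.

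Both rules can set aside readings that were validly obtained, although a random-effects model does not need balanced data. In a device reliability study, a reading may be missing because the landmark was hard to find. If so, leaving out the affected people or sites would make the device look more reliable than it is, and nothing in the planned report would show it.

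**Working it through.** **1. Readings at stake.** From sections 5.1 and 10.1: 4 sites, 4 repetitions, 3 observers.

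- Rest readings per participant: 4 × 4 × 3 = 48. Because exercise comes last, a participant who stops on the treadmill can have all 48. Section 9.2.1 names dyspnoea, falls and exhaustion as possible events there. Both sections would replace this person, and a complete set of 35 implies that the 48 readings are left out.
- One observer missing at all four sites: the other two observers lose 2 × 4 = 8 readings from the primary ICC, and 2 × 4 × 4 = 32 from the four-repetition average. If only one site is affected, the primary ICC loses 2.

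**2. The plan's own figure.** Section 4.4 states "a one-sided 95% target confidence interval width of 0.05 based on three observers, a sample size of 140 is required", with expected ICC r = 0.8. The Bonett formula is

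n = 8 z² (1 − r)² (1 + (k − 1) r)² / [k (k − 1) w²] + 1.

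With z = 1.96, k = 3 and full width w = 0.10 (0.05 on each side): 8 × 3.8415 × 0.04 × 6.76 / (6 × 0.01) + 1 = 139.5, rounded up to 140; 140 / 4 = 35 participants. The figure reproduces.

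**3. Reserve against the 0.75 limit.** The half-width is z × √{2 (1 − r)² (1 + (k − 1) r)² / [k (k − 1)(n − 1)]}. The table treats samples as independent, as the protocol does. The loss rates are assumptions, since the documents give none.

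| Samples lost, not replaced | n | Half-width | Expected lower bound |
|---|---|---|---|
| 0% | 140 | 0.0499 | 0.750 |
| 5% | 133 | 0.0512 | 0.749 |
| 10% | 126 | 0.0526 | 0.747 |
| 20% | 112 | 0.0559 | 0.744 |

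The loss of precision is small, but it starts from a bound that sits on the limit.

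**4. Selection, illustrated.** All inputs in this step are assumed. Write ICC = S / (S + e), with S the between-subject variance and e the error variance.

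- Suppose S = 0.8 and e = 0.2 in readily measured people (ICC 0.80), and a share f has m times the error variance. The all-comer error is 0.2 × [(1 − f) + f m]. For f = 5%, m = 2 it is 0.21, and the ICC is 0.8 / 1.01 = 0.792. For f = 20%, m = 3 it is 0.28, and the ICC is 0.8 / 1.08 = 0.741. Measuring only the easy group would overstate the ICC by 0.008 to 0.059.
- Conversely, suppose the all-comer ICC is 0.75 (S = 0.75, mean error 0.25) and every hard-to-measure person is replaced. The remaining error is e0 = 0.25 / [(1 − f) + f m]. For f = 10%, m = 3: e0 = 0.208 and the ICC is 0.783. For f = 10%, m = 5, or f = 20%, m = 3: e0 = 0.179 and the ICC is 0.808. The shift is 0.033 to 0.058.
- The result follows the inputs. In the first set-up, f = 20% with m = 5 gives 0.8 / 1.16 = 0.690, a shift of 0.11.

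**5. Are gaps plausible?** Section 3 gives a 60-minute visit; sections 4.4 and 8.5 give 90 minutes, and these must be reconciled. Five minutes of rest plus two rounds of 5 minutes' walking and 5 minutes' post-exercise measurement take 25 minutes. That leaves 35 to 65 minutes for 48 rest readings. If they are taken one after another, this is 44 to 81 seconds each, before questionnaires and changes of observer.

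**The case against.** A reader might infer that the plan deletes all partial data and so estimates reliability only in fully measurable people. Section 8.5 does not say that. It tolerates one missed repetition, excludes data only from the affected analysis, and leaves partly measured people in the others. Strict completeness follows only from section 4.4.

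It is also tempting to put the cost of a missing observer at 32 readings throughout. In the primary ICC it is 8 at most, and the other two observers' readings remain in their own intra-observer analyses.

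Nor do the documents support a firm claim of upward bias. The scenarios assume the share of difficult people, their error variance, that all of them are lost and nobody else is, and that S is unchanged. If only half of a difficult 10% is replaced, the second set-up gives 0.765 (m = 3) or 0.776 (m = 5). If difficult people also have extreme compressibility, leaving them out lowers S: with f = 10% and m = 3, a fall from 0.75 to 0.625 gives 0.625 / 0.833 = 0.75, which cancels the shift, and a larger fall reverses it. A failed treadmill bout says little about landmark difficulty.

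Losses may well be few: there is one session without follow-up, and people with leg pathology or unable to exercise for five minutes are excluded. The second rule in section 8.5 can also be read as a fallback for isolated gaps, at a different level from participant withdrawal.

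These points stand, and they limit the claim about size. They do not reconcile the two sections, and they give no reason to discard valid readings or to leave failures unreported.

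**Conclusion.** The concern holds in a limited form. Sections 4.4 and 8.5 do not describe one data set, and both can discard valid readings: up to 48 rest readings for a participant who stops during exercise, and 8 primary readings (32 in the averaged analysis) when one observer is missing at all four sites. Upward bias is possible if missingness is linked to difficulty of measurement, but neither its direction nor its size can be established from the documents. The shift of about 0.01 to 0.06 rests wholly on assumed shares and error ratios. The point deserves action because the expected lower bound is already at the limit, so small shifts can change the classification.

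**What to change.** - Make sections 4.4 and 8.5 agree on one replacement trigger and one analysis set.
- Keep every obtained reading, including the rest readings of participants who stop early, even if they are replaced.
- Drop the exclusion rule in section 8.5. Fit the planned two-way random-effects model by REML to all available readings: first readings for the primary ICC, and all repetitions where those are analysed. State what counts as the first reading if the first attempt fails.
- Name in advance a confidence-interval method for unbalanced data, for example a parametric or participant-level bootstrap. The latter does not resample the three observers, so the choice should be explained.
- Report the complete-case ICC as a sensitivity analysis, with category and the unit of exclusion defined for it.
- Report the number and reasons of failed, missing and replaced measurements by site and observer.

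The cost is protocol and SAP wording, slightly more analysis work and the choice of an interval method; no new participants or procedures are needed. REML does not recover readings that could not be obtained, so the failure counts must stand beside the ICC.
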